**Exclusion Criteria:**

1. Involvement in the planning and/or conduct of the study (applies to both AstraZeneca staff and/or staff at the study site) or previous enrollment or randomization in the present study
2. Participation in another clinical study with an investigational product during the last 3 months
3. Any previous treatment with a PD1 or PD-L1 inhibitor, including MEDI4736
4. Receipt of the last dose of anti-cancer therapy (chemotherapy, immunotherapy, endocrine therapy, targeted therapy, biologic therapy, tumor embolization, monoclonal antibodies, other investigational agent) 30 days prior to the first dose of study drug, and 30 days prior

to the first dose of study drug for subjects who have received prior TKIs [e.g., erlotinib, gefitinib and crizotinib] and within 6 weeks for nitrosourea or mitomycin C).

5. Current or prior use of immunosuppressive medication within 28 days before the infusion with MEDI4736 or MEDI4736 + tremelimumab and through 90 days post infusion, with the exceptions of intranasal and inhaled corticosteroids or systemic corticosteroids at physiological doses, which are not to exceed 10 mg/day of prednisone, or an equivalent corticosteroid.
6. Any unresolved toxicity (>CTCAE grade 2) from previous anti-cancer therapy.
7. Any prior Grade  $\geq 3$  immune-related adverse event (irAE) while receiving any previous immunotherapy agent, or any unresolved irAE >Grade 1
8. Active or prior documented autoimmune disease within the past 2 years NOTE: Subjects with vitiligo, Grave's disease, or psoriasis not requiring systemic treatment (within the past 2 years) are not excluded.
9. Active or prior documented inflammatory bowel disease (e.g., Crohn's disease, ulcerative colitis)
10. History of primary immunodeficiency
11. History of allogeneic organ transplant
12. History of hypersensitivity to MEDI4736 or any excipient
13. History of hypersensitivity to tremelimumab or the combination of MEDI4736 + tremelimumab
14. Uncontrolled intercurrent illness including, but not limited to, ongoing or active infection, symptomatic congestive heart failure, uncontrolled hypertension, unstable angina pectoris, cardiac arrhythmia, active peptic ulcer disease or gastritis, active bleeding diatheses including any subject known to have evidence of acute or chronic hepatitis B, hepatitis C or human immunodeficiency virus (HIV), or psychiatric illness/social situations that would limit compliance with study requirements or compromise the ability of the subject to give written informed consent
15. Known history of previous clinical diagnosis of tuberculosis
16. History of leptomeningeal carcinomatosis
17. Receipt of live attenuated vaccination within 30 days prior to study entry or within 6 months of receiving MEDI4736 or MEDI + tremelimumab

18. Receipt of drugs with laxative properties and herbal or natural remedies for constipation within 90 days of receiving MEDI4736 or MEDI + tremelimumab
19. Receipt of sunitinib within 3 months of receiving tremelimumab
20. Female subjects who are pregnant, breastfeeding, or male or female subjects of reproductive potential who are not employing an effective method of birth control
21. Any condition that, in the opinion of the investigator, would interfere with the evaluation of the study treatment or interpretation of subject safety or study results
22. Symptomatic or uncontrolled brain metastases requiring concurrent treatment, inclusive of but not limited to surgery, radiation, and/or corticosteroids.
23. Subjects with uncontrolled seizures
24. N3 nodal disease
25. History of interstitial lung disease/pneumonitis
26. No tissue is obtainable at the time of thoracoscopy.
27. Intraabdominal malignancy discovered at laparoscopy and proven pathologically, or nodal disease discovered at mediastinoscopy (N2 or N3 disease) and proven pathologically

**Investigational Product(s), Dose and Mode of Administration:**

MEDI4736, 15 mg, IV infusion once prior to resection

Or: Subjects will be administered MEDI4736 (1500 mg intravenously) + tremelimumab (75 mg intravenously) once during the study.

Subjects under 30 kg will be treated with weight-based dosing for both MEDI4736 and Tremelimumab combination therapy. These patients are excluded from fixed based dosing to limit endotoxin exposure from the drug preparations.

**Study Assessments and Criteria for Evaluation:**

**Safety Assessments:**

On the infusion day with MEDI4736 or MEDI4736 + tremelimumab, we will conduct clinical chemistry, hematology, and vitals. Subjects will be followed for 90 days after the last dose for safety to monitor any AEs, SAEs, etc.

### **Efficacy Assessments:**

#### **PRIMARY ENDPOINTS**

- 1) Intratumoral CD8/Treg ratio determined by CyTOF.

#### **SECONDARY ENDPOINTS**

- 1) Percentage of ICOS+ CD4 T cells will be determined by CyTOF in blood, tumor, and bone marrow
- 2) PD-L1 expression will be determined in tumor tissue by IHC (Ventana assay); PD-L1 will also be determined on immune cell subsets by CyTOF in blood, tumor, and bone marrow.
- 3) NanoString gene expression arrays will be used to compare the gene expression of 300 immune-related genes in frozen tumor tissue obtained preoperatively and postoperatively.
- 4) Overall and recurrence-free survival survival will be measured according to our usual routine follow-up protocol and compared with historical controls. These analysis will be post-protocol analysis based upon data obtained from the standard of care follow up in our post-surgical patients.
- 5) A comprehensive evaluation of immune cell composition and phenotype will performed in preoperative and postoperative tumor tissue and peripheral blood, as well as bone marrow. **Appendix C** outlines the complete CyTOF panel that will be used for each individual specimen. Substudies will include:
  - a. Changes in T-cell subset (i.e., CD4, CD8, FoxP3) frequency and memory and activation phenotype (i.e., CD25, CD127, CD45RA, CD62L, CCR4, CCR6, Tim1).
  - b. Changes in the T-cell polarization state (intracellular interferon-gamma, TNF-alpha, IL-17, IL-2).
  - c. Changes in myeloid cell composition: dendritic cell, macrophage, MDSC, neutrophil (i.e., HLA-DR, CD11c, BDCA-1, BDCA-2, BDCA-3, BDCA-4, CD68, CD163, CD206, CD66b, CD15).
  - d. Changes in NK cell and NK T-cell composition (i.e., CD56, CD3, V224, Vbeta1)

For all experiments requiring tissue, whereas relatively large tissue samples are generally obtainable from both pre-resection biopsies performed by thoracoscopy, and at the time of tumor resection, our experiments will be prioritized as follows:

- 1) CyTOF
- 2) IHC
- 3) Gene expression

### **Statistical Methods and Data Analysis:**

There will be two treatment arms (MEDI4736 only and combination MEDI4736+tremelimumab) and one untreated arm (control). Randomization, stratified by receiving previous chemotherapy or not, will help to minimize patient selection biases between three arms. Preliminary tests will be performed to assess whether our data is normally or non-normally distributed. Patient characteristics will be summarized descriptively. Baseline characteristics will be compared by treatment assignment. For our primary objective that compares outcome variable in tissues before and after treatment with combination MEDI4736 and tremelimumab, we will use a paired t-test in log-transformed ratio of intratumoral cytotoxic T cells to regulatory T cells (CD8/Treg) before and after the treatment. In our secondary objective numerous variable comparisons are made between tumor tissues from untreated patients with from patients undergoing treatment with either MEDI4736 or MEDI4736 + tremelimumab, and between tumor tissues from patients undergoing treatment with MEDI4736 and tumor tissues from patients undergoing treatment with MEDI4736+tremelimumab. In these comparisons, a paired t-test or Student t-tests will be performed. Because approximately 20 comparisons of immune cell populations will be performed, a Bonferroni correction will be applied to correct for multiple comparisons. For the comparison of overall survival and recurrence-free survival between treatment groups, log-rank test will be used. These analysis will be post-protocol analysis based upon data obtained from the standard of care follow up in our post-surgical patients. SAS software will be used for all other statistical analyses.

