- 5) Comparison of tumor tissue expression (Ventana assay) of programmed death-ligand 1 (PD-L1) in patients treated with combination therapy (MEDI-4736 and Tremelimumab) compared to either patients treated with MEDI-4736 alone, and separately compare to untreated patients.
- 6) Comparison of overall survival in patients treated with either MEDI-4736 alone or MEDI-4736 plus Tremelimumab with historical untreated controls. These analysis will be post-protocol analysis based upon data obtained from the standard of care follow up in our post-surgical patients.
- 7) Comparison of recurrence-free survival in patients treated with either MEDI-4736 alone or MEDI-4736 plus Tremelimumab with historical untreated controls. These analysis will be post-protocol analysis based upon data obtained from the standard of care follow up in our post-surgical patients.

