Tumor tissues obtained either by thorascopic biopsy or by resectional surgery will be evaluated by time-of-flight mass spectrometry (CyTOF) to determine intratumoral CD8/Treg ratios and percentage of ICOS positive CD4 T cells, and by immunohistochemistry (Ventana assay) to determine the tissue expression of PD-L1. These variables will be compared before and after treatment (changes within the same patient tumor), or between treatment groups (MEDI-4736 alone, MEDI-4736+tremelimumab, untreated) following treatment. Additional hypothesis-generating analyses will include a comprehensive systems based evaluation of the intratumoral immune cell population composition and phenotype [e.g., dendritic cells, macrophages, myeloid derived suppressor cells (MDSC), neutrophils, T-cell subsets, natural killer (NK) cells, and B cells], and immune-related gene expression using the nanostring system within the tumors, blood, and bone marrow of patients in all treatment groups.

**Number of Centers:** 1

**Number of Subjects:** 20

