**Females:**

$$\text{Creatinine CL} = \frac{\text{Weight (kg)} \times (140 - \text{Age})}{72 \times \text{serum creatinine (mg/dL)}} \times 0.85$$

5. Female subjects must either be of non-reproductive potential (i.e., post-menopausal by history:  $\geq 60$  years old and no menses for  $\geq 1$  year without an alternative medical cause; OR history of hysterectomy, OR history of bilateral tubal ligation, OR history of bilateral oophorectomy) or must have a negative serum pregnancy test upon study entry.
6. Subject is willing and able to comply with the protocol for the duration of the study including undergoing treatment and scheduled visits and examinations including follow up.
7. Surgically resectable MPM with no disease extension beyond the ipsilateral hemithorax
8. Planned resectional surgery for MPM [extrapleural pneumonectomy (EPP) or pleurectomy and decortication (P/D)]
9. Any MPM histology (epithelial, mixed, sarcomatoid)
  - a. N0 or N1 nodal disease, as present on preoperative chest CT and/or PET/CT
  - b. N2 nodal disease if no progression after 2 cycles of standard chemotherapy. Progression will be considered if additional N1 or N2 disease develop during chemotherapy.

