efficacy of combination PD-L1 and CTLA-4 blockade compared with a single-agent therapy. PD-L1 is expressed with a relatively high frequency in a broad range of human malignancies, up to 88% in some cancers. In a number of these cancers, including lung (Mu et al., 2011), renal (Krambeck et al., 2007), pancreatic (Nomi et al., 2007), and ovarian cancer (Hamanishi et al., 2007), the expression of PD-L1 is associated with reduced survival and an unfavorable prognosis. PD-L1 is expressed in a substantial proportion of MPM tumors (21% of epithelial MPM tumors and 74% of non-epithelial MPM tumors), and its expression is associated with a decreased overall survival (Mansfield et al., 2014). Although it appears that the selection of patients based on PD-L1 expression within the tumor microenvironment may improve the probability and/or quality of responses to PD-1 pathway -targeting agents, there remain a number of patients with PD-L1-negative tumors that respond to the blockade with the PD-L1 inhibitor MEDI4736 (Brahmer et al., 2014). Furthermore, the expression of PD-L1 may not have as much of an impact when a combination of checkpoint inhibitors is utilized. For example, a study investigating the combination of a PD-1 inhibitor (nivolumab) and a CTLA-4 inhibitor (ipilimumab) in patients with melanoma suggested that the combination of CTLA-4 and PD-1 blockade may have an effect independent from tumoral PD-L1 expression (Wolchok et al., 2013). Interestingly, in mouse models of melanoma, PD-1 blockade increased the expression of CTLA-4 on intratumoral T cells, and reciprocally, CTLA-4 blockade increased PD-1 expression on intratumoral T cells. This finding may provide an explanation for the synergistic activities of these two drugs, and we expect to uncover similar findings in human MPM tumors after treating patients with these drugs.

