## **TREATMENT PLAN**

### **5.3 Subject enrollment and randomization**

We expect to enroll a total of 20 evaluable subjects (if tissue obtained at time of thoracoscopy and time of surgical resection) with surgically resectable MPM to this study over a period of 24 months. Subjects will be randomized. Subjects will be assigned to one of the three treatments (n = 8 MEDI4736, n = 8 MEDI4736 + tremelimumab, and n=4 control). All subjects will undergo surgical resection one to six weeks after the infusion.

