#### **5.3.1 Procedures for randomization**

After mediastinoscopy + thoracoscopy, eligible subjects with MPM will be randomized in 2:2:1 ratio to one of three arms: MEDI4736 alone, MEDI4736 + tremelimumab, and a control group of neither MEDI4736 nor tremelimumab. A computer-generated randomization scheme may be generated by the Biostatistics Core, Baylor College of Medicine. Randomization will be accomplished via access to a secure website developed by the Biostatistics Core and automatically notified to the study coordinator or the investigator via email. Randomization will be stratified by receiving previous chemotherapy or not.

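### The between-arm PD-L1 comparisons use unadjusted t-tests and so give up some precision that adjusting for tumour histology, which the trial already records, would recover

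*Combined protocol and SAP*

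**What the plan says.** Objective 5 (synopsis, section 2.2 and section 8.1.2) is a "Comparison of tumor tissue expression (Ventana assay) of programmed death-ligand 1 (PD-L1) in patients treated with combination therapy" against MEDI4736 alone and, separately, against untreated patients. The Study Design text in the synopsis and section 3.1 place this comparison "between treatment groups (MEDI-4736 alone, MEDI-4736+tremelimumab, untreated) following treatment". Section 5.3 sets the arms at "n = 8 MEDI4736, n = 8 MEDI4736 + tremelimumab, and n=4 control".

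For the secondary comparisons, the synopsis and section 10.3 name only two tests: "In these comparisons, a paired t-test or Student t-tests will be performed". Neither contains a model or a covariate. Baseline characteristics are to be summarised and compared by arm, but the result does not enter any estimate.

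Inclusion criterion 9 admits "Any MPM histology (epithelial, mixed, sarcomatoid". Section 1.4 gives PD-L1 expression in "21% of epithelial MPM tumors and 74% of non-epithelial MPM tumors". Section 5.3.1 states: "Randomization will be stratified by receiving previous chemotherapy or not"; no other stratification factor is named. Section 7.1.2 says the pre-treatment thoracoscopy supplies tissue to confirm the diagnosis, section 7.3.3 that tumour is sampled before treatment and at resection, and section 13 that histology is in the data set.

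**The concern.** On the protocol's own figures, histology separates tumours by 74 - 21 = 53 percentage points in PD-L1 expression. In arms of 4 to 8 patients the mix of histologies will often differ by chance, and an unadjusted comparison leaves that variation in the estimate and in its standard error. Objective 5 is the randomised check of the hypothesis in section 1.4 that adding tremelimumab raises tumour PD-L1, so precision lost here bears on a stated question of the trial. A strong predictor that is already recorded goes unused.

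**Working it through.** **The plan's own figure.** The documents give no power or sample size for PD-L1. Their only power statement is for the primary paired test: n = 8, change 2.87 - 1.94 = 0.93, SD of change 0.808, two-sided 5%. The noncentral t distribution gives 79.7%, which reproduces the stated 80%. It says nothing about objective 5.

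**Inputs.** From the documents: 21% and 74% (section 1.4); arms of 8, 8 and 4 (section 5.3). Assumed: PD-L1 is scored positive or negative, because the scale of the Ventana endpoint is not defined; the share q of non-epithelial tumours is 20-40%, with 10% as a low case, because no mix is given.

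**Variance due to histology.** With p = 0.21(1 - q) + 0.74q, the share explained is R² = q(1 - q) × 0.53² / [p(1 - p)]. At q = 0.30:
- p = 0.147 + 0.222 = 0.369, and total variance = 0.369 × 0.631 = 0.2328
- between-histology variance = 0.21 × 0.2809 = 0.0590
- R² = 0.0590 / 0.2328 = 0.253

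**Standard error of the arm difference.** Unadjusted: sqrt[p(1 - p)(1/n1 + 1/n2)]. Adjusted in a two-arm model: the same × sqrt(1 - R²) × sqrt[1 + 1/(N - 4)], where the last factor is the price of estimating the covariate. At q = 0.30:
- 8 v 8: sqrt(0.2328 × 0.25) = 0.241; adjusted 0.241 × 0.864 × 1.041 = 0.217
- 8 v 4: sqrt(0.2328 × 0.375) = 0.295; adjusted 0.295 × 0.864 × 1.061 = 0.271

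| q | R² | 8 v 8: SE unadjusted / adjusted | excess | 8 v 4: SE unadjusted / adjusted | excess |
|---|---|---|---|---|---|
| 10% | 13% | 0.220 / 0.214 | 3% | 0.270 / 0.267 | 1% |
| 20% | 21% | 0.232 / 0.215 | 8% | 0.285 / 0.269 | 6% |
| 30% | 25% | 0.241 / 0.217 | 11% | 0.295 / 0.271 | 9% |
| 40% | 28% | 0.247 / 0.219 | 13% | 0.302 / 0.273 | 11% |

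Simulation of the two-arm comparisons (20,000 runs per setting, q = 20%, 30%, 40%) gives unadjusted / adjusted SDs of 0.232/0.215, 0.240/0.216 and 0.247/0.219 for 8 v 8, and 0.284/0.265, 0.297/0.271 and 0.302/0.272 for 8 v 4. The unadjusted SD is therefore 8-13% and 7-11% larger. One model on all 20 patients (40,000 runs per setting) cuts the SD by 8-12% in both contrasts.

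**Interval width, with the lost degree of freedom counted (two-arm formula).** At q = 0.30 the 95% half-width goes from 51.7 to 46.9 points (8 v 8) and from 65.8 to 61.3 points (8 v 4). Over q = 20-40% the narrowing is 7-11% and 4-8%. At q = 10% it is 2% and none.

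**How much histology moves a single trial.** The chance shift in the PD-L1 difference has SD 53 × sqrt[q(1 - q)(1/n1 + 1/n2)] points. At q = 0.30 this is 12.1 (8 v 8) and 14.9 (8 v 4). By exact binomials over q = 20-40%, the arms differ by at least 25 points in non-epithelial share with probability 34-44% (8 v 8) or 45-54% (8 v 4). A 25-point gap moves PD-L1 by 0.25 × 53 = 13 points. The average shift over simulated randomisations is about zero.

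**The case against.** A reader might infer that an apparent tremelimumab effect on PD-L1 could simply be a histology difference, so that the t-test misleads. The documents do not support this. Patients are randomised, so chance imbalance is random error, and the t-test's standard error already counts it. Simulating the same positive/negative model with no treatment effect (8,000 runs per setting, q = 20-40%) gave false-positive rates of 5-7% (8 v 8) and 6-7% (8 v 4), close to nominal. The imbalance probabilities mostly describe variance the test already includes. This objection stands in full and limits the point to precision.

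Other objections stand in part:
- The size rests on assumptions. The 21% and 74% are proportions of tumours from a cited study, applied here to tissue taken after treatment. If PD-L1 is analysed as a continuous score, the variance explained by histology is unknown.
- The gain is modest, and intervals of roughly ±45 to ±60 points remain wide. In that simulation the interval narrowed by 9-13% on average, but the adjusted interval was wider in about 26-39% of single trials.
- Pre-treatment PD-L1 is the more direct covariate and would probably capture much of the histology effect. Section 10 describes the secondary PD-L1 endpoint as measured before and after each treatment. If arms were compared on change, a histology effect that is constant on that scale would cancel. However, the Study Design text puts the between-arm comparison after treatment, and no analysis of change between arms is specified.
- Comparing baseline characteristics by arm would probably reveal an imbalance in histology, but it does not alter the estimate.

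**Conclusion.** The point holds as a loss of precision in a secondary comparison of a self-described pilot study. Under a positive/negative score and 20-40% non-epithelial tumours, the unadjusted standard error is about 7-13% larger than the adjusted one (the closed form puts the lowest case, 8 v 4 at 20%, at 6%). At 10% non-epithelial the excess is about 3% or less, and the 8 v 4 interval does not narrow at all. The t-test is neither biased nor invalid.

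Two further inferences would also go too far. The primary paired test and objective 2 compare each patient with himself or herself, and histology is constant within a patient, so neither is affected. Nor does the point show that randomisation should have been stratified by histology: two binary factors give four strata of about 20/4 = 5 patients spread over three arms, which is too sparse to work well. The remedy belongs in the analysis.

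**What to change.** In section 10.3 and the synopsis, replace the Student t-test for objective 5 by one prespecified linear model fitted to all three arms: post-treatment PD-L1 on arm and histology (epithelial v non-epithelial), with pre-treatment biopsy PD-L1 as an additional or alternative covariate. State which covariates are used before any PD-L1 data are seen; the study is open-label, and adjustment chosen after an imbalance appears would look data-driven. Report the two planned contrasts, combination v MEDI4736 alone and combination v untreated, and show histology by arm beside them.

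Define histology as that of the pre-treatment biopsy. Section 13 shows that histology is held but not from which specimen, and resection tissue is post-treatment. State the scale on which the Ventana result is analysed. If every patient in the model has the same histology, the term drops out.

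The cost is SAP wording, with no new patients or procedures. Each covariate takes one degree of freedom, and in some single trials the interval will be slightly wider. With histology alone the three-arm model leaves 20 - 3 - 1 = 16 residual degrees of freedom, against 14 and 10 for the separate t-tests, at the price of assuming a common residual variance across the three arms.

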### **Sample Size Determination:**

The primary objective is comparison of the ratio of CD8/Treg before and after treatment with combination MEDI4736+Tremelimumab. A total of 20 evaluable subjects will be enrolled in this study for 24 months and 8 subjects will be assigned to combination MEDI4736+Tremelimumab (8 subjects to MEDI4736 only and 4 subjects to control). The outcome of interest in this study is a change in ratio of CD8/Treg before and after treatment with combination MEDI4736+Tremelimumab within subjects. Our sample size was therefore calculated based upon the change in CD8/Treg ratio in tumor tissues before and after treatment with combination MEDI4736+Tremelimumab therapy. This sample size calculation is also applicable to our secondary objectives including the change in CD8/Treg ratio in tumor tissues before and after treatment with MEDI4736 monotherapy.

Because there are no data available to estimate a change of ratio of CD8/Treg before and after the treatment in MPM, we utilized data from preclinical reports, and clinical data in melanoma patients. The ratio of CD8 T cells to regulatory T cells (CD8/Treg) is increased by the blockade of CTLA-4 and PD-1 within B16 mouse melanoma tumors (CD8/Treg ratio 2 in untreated, 11 in  $\alpha$ CTLA-4 treated, and 8 in  $\alpha$ PD-1 treated) (Curran et al., 2010), and this ratio is predictive of therapeutic efficacy in this model (Quezada et al., 2006). In a recent report of melanoma patients undergoing PD-1 blockade, subjects who had a significant clinical response were found to have an increase in the number of intratumoral CD8 T cells following drug delivery ( $15.1 \pm 6.6$  to  $36.0 \pm 8.4$  CD8 T cells/mm^2) (Tumeh et al., 2014). Further, our pilot data from 6 subjects with MPM the log transformed ratio of CD8/Treg was approximately normally distributed with a mean of 1.94(6.96 in raw scale) and standard deviation of 0.808(2.24 in raw scale). Assuming that repeat values are moderately correlated( $r=0.5$ ), then the difference between before and after the combination treatment will also have a standard deviation of 0.808(2.24 in raw scale). We estimate that we will have 80% power ( $\alpha=5\%$ , a paired t-test) to detect an increased log ratio CD8/Treg of 2.87(17.71 in raw scale) after the combination treatment with 8 subjects.

Clinical Study Protocol

Drug Substance Tremelimumab

Study Number **ESR-14-10744**

Edition Number 8

Date 17 April 2019

